5.0 Study Design*

- 5.1 Describe and explain the study design (e.g. case-control, cross-sectional, ethnographic, experimental, interventional, longitudinal, observational).

Response: Randomized double -blind placebo controlled cross over study.
Randomization-Patients will be assigned to the study product using a random numbers table. Both the placebo rinse and the “active “test rinses” will be provided by the sponsor in similar bottles labeled with a code label for each bottle. The code and patient numbers will be kept in a sealed cabinet in [name]. The code will only be broken if there is need to identify a patient with adverse effects which may be attributed to the rinse they were given.

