8.0 Inclusion and Exclusion Criteria

Response: The number of subjects needed for this study is based on the feasibility of the study. *Inclusion and Exclusion Criteria**

8.1 *Describe the criteria that define who will be **included** in your final study sample.*

NOTE: This may be done in bullet point fashion.

Response: Individuals may be included in the study provided they meet all of the following inclusion criteria:

- Must have read, understood and signed an informed consent prior to being entered into the study,
- Must be 18 to 80 years of age, male or female,
- Have at least 20 natural or restored teeth,
- Have a complaint of xerostomia,

- Have an unstimulated salivary flow rate <0.20 ml/minute which represents a significant reduction of normal salivary function, 6) Must have subjective xerostomia symptom: minimum level of 4 on a 10 centimeters Visual Analog Scale (VAS). The question, using a VAS scale, would be "How would you score your dryness on the basis of a scale of 1 to 10?" and on the left would be zero, and on the right would be severe (10). They would have to score a 4 or higher to be in the study. We would ask this same question both before and after the two week usage period,
- Agree not to have a dental prophylaxis or any other elective, non-emergency dental procedures (other than those provided during the study) any time during the study,
- Agree to abstain from the use of any products for xerostomia other than those provided in the study
- Agree to comply with the conditions and schedule of the study.

8.2 Describe the criteria that define who will be **excluded** from your final study sample.

NOTE: This may be done in bullet point fashion.

Response: Individuals are not eligible for participation in this study if any of the following are noted:

- Physical limitations or restrictions that might preclude normal tooth brushing.
- Evidence of gross oral pathology, including widespread caries or chronic neglect, extensive restoration, pre-existing gross plaque or soft or hard tissue tumor of the oral cavity.
- Presence of severe gingivitis with 30 or more sites showing bleeding on probing.
- Evidence of major oral hard or soft tissue lesions or trauma at the baseline visit as determined by the Investigator/Examiner.
- Chronic disease with concomitant oral manifestations other than xerostomia

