12.0 Procedures Involved*

12.1 Provide a description of **all research procedures or activities** being performed and when they are performed once a subject is screened and determined to be eligible. Provide as much detail as possible.

NOTE: This should serve as a blueprint for your study and include enough detail so that another investigator could pick up your protocol and replicate the research. For studies that have multiple or complex visits or procedures, consider the addition of a schedule of events table in in your response.

Response: **If a potential patient is a mouthrinse user, we will be sending them a Consent Form for the study which they will be asked to read, sign and date and return to us. Also, If they have any concerns or questions, we will discuss with them. Once we receive the signed consent form, we will give patients a screening visit appointment, and remind them to cease use of any mouthrinses for 7 days prior to the appointment.** At the screening visit, every potential subject will be consented again and interviewed. Subjects who sign the Informed Consent Form and meet eligibility criteria will then have an Oral Screening Examination by the Primary Examiner. After review of the results of the Informed Consent, Screening Interview and Screening Oral Examination, the Principal Investigator or designee will determine whether or not a subject should be enrolled in the study.

Screening

Seven days before screening visit potential subjects shall stop using their usual dry mouth mouthrinse as outlined above.. Male and female subjects will again read and sign the informed consent with a staff member of the study as a witness.. Since some mouthrinses have a residual effect on oral tissues, we are asking the potential subjects to cease using these products for one week prior to their visit so that we can evaluate the status of their oral tissues . Interested patients will be contacted at least 7 days prior to the screening visit to read, sign and date the Consent Form and then start the one week withdrawal of current mouthrinse

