At the end of Visit 4 (examination for the second product) they will go through a 1 week wash out period and then return for Visit 5 (baseline for the third product) and study will be completed in visit 6.

12.2 Describe what data will be collected.

NOTE: For studies with multiple data collection points or long-term follow up, consider the addition of a schedule or table in your response.

Response: The various data collection points are shown in Table 1 (Study Schedule).

Events	Screening	Visit 1	Visit 2	Visit 3	Visit 4	Visit 5	Visit 6
		First product		Second product		Third product	
Informed Consent, Demographics, Inclusion/Exclusion Criteria, Medical History, Concurrent meds	X						
Demographics Questionnaire	X						
Oral Soft/Hard Tissue Exam & Photos		X	X	X	X	X	X
Update of Inclusion/Exclusion Criteria, Medical History and Conmeds		X	X	X	X	X	X
Unstimulated saliva flow	X (<0.2)	X	X	X	X	X	X
VAS	X (>=4)	X	X	X	X	X	X
Questionnaires (Xerostomia, QoL)		X	X	X	X	X	X
Objective xerostomia endpoint (ROAG)		X	X	X	X	X	X
Product Distribution		X	X	X	X	X	X
Diary Disbursement		X		X		X	
Compliance Check			X		X		X
Product Attribute Questionnaire			X		X		X
Immediate Post-Rinse Evaluation			X		X		X
Adverse Events			X	X	X	X	X

12.3 List any instruments or measurement tools used to collect data (e.g. questionnaire, interview guide, validated instrument, data collection form).

Include copies of these documents with your submission.

Response:

- a. Demographics Questionnaire
- b. Intraoral camera
- c. Medical History
- d. VAS question (Appendix A),
- e. Xerostomia questionnaire (Appendix B)
- f. Oral Health Impact Profile -14 (OHIP-14) (Appendix C)
- g. Revised Oral Assessment Guide (ROAG) (Appendix D)
- h. Daily Diary (Appendix E)
- i. Product Performance and Attributes Questionnaire for the first product (Appendix F)
- j. Immediate Post-Rinse Evaluation (Appendix G)
- k. Oral soft and hard tissue examination form
- l. *Unstimulated saliva flow measurement form*
- m. *Adverse Events form*

12.4 Describe any source records that will be used to collect data about subjects (e.g. school records, electronic medical records).

Response: No source records will be used to collect data about subjects.

12.5 Indicate whether or not **individual** subject results, such as results of investigational diagnostic tests, genetic tests, or incidental findings will be shared with subjects or others (e.g., the subject's primary care physician) and if so, describe how these will be shared.

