19.0 Data Management and Analysis*

19.1 *Describe the data analysis plan, including any statistical procedures. This section applies to both quantitative and qualitative analysis.*

Response: This is a randomized double-blind placebo controlled crossover study comparing the HYDRAL Oral rinse to Biotene rinse, and HYDRAL Oral rinse to placebo. A one-week wash-out period will be adopted between phases to eliminate any possible carry-over effect of a treatment from previous phase. The primary endpoint is a reduction of dry mouth symptom in VAS (0-10 scale). To control for the Type I error rate of incorrectly rejecting the null hypothesis, a two-sided significance level of 0.025 will be used. A power analysis for a crossover study estimated that with 80% power, 33 subjects will be required to detect a minimal difference in mean VAS of 0.8. To account for withdrawal and other factors (e.g. failed measurement), a total of 39 subjects will be recruited and randomized into the study.

Descriptive statistics for all subjects will be performed for background and demographic variables. Continuous variables are expressed as frequencies (n), mean +/- SD and categorical variables are expressed as frequencies (n) and percentages (%). To evaluate the primary end point, an Analysis of variance will be applied to examine the possible residual or carryover effects of treatments. If no residual effect is found, paired t test or Wilcoxon sign-rank test where appropriate, will be used to compare treatments; however, if residual effect is significant, a mixed model (with unstructured covariance matrix) will be performed with treatment, period,

and interaction of treatment and period as fixed effects to account for treatment, period, and carryover effect. For categorical variables, percent or proportion of subjects will be calculated and a Chi-square test or McNemar test will be used. All statistical tests will be conducted using SAS version 9 (SAS Institute Inc. Cary, NC).

19.2 *If applicable, provide a power analysis.*

NOTE: This may not apply to certain types of studies, including chart/records reviews, survey studies, or observational studies. This question is asked to elicit whether the investigator has an adequate sample size to achieve the study objectives and justify a conclusion.

Response: The number of subjects needed for this study with adequate power is based on a power analysis of 0.8.

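### The carryover model in Section 19.1 has no term for the preceding product and names no contrast, so its estimate is not carryover-adjusted as the plan claims

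*Combined protocol and SAP*

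**What the plan says.** Section 19.1 presents the washout as the first protection: "A one-week wash-out period will be adopted between phases to eliminate any possible carry-over effect of a treatment from previous phase". It then sets a two-stage rule for the primary endpoint. First, "an Analysis of variance will be applied to examine the possible residual or carryover effects of treatments". If nothing is found, a "paired t test or Wilcoxon sign-rank test where appropriate, will be used to compare treatments". If the residual effect is significant, the plan moves to a mixed model with unstructured covariance, containing treatment, period, "and interaction of treatment and period as fixed effects to account for treatment, period, and carryover effect".

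The significance level and terms of the ANOVA are not given, nor is the contrast to be taken from the mixed model.

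On the orders, Section 5.1 says only that "Patients will be assigned to the study product using a random numbers table". Section 22.3 refers to randomization codes supplied by a third party.

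On the endpoint, Sections 3.0 and 19.1 speak of a reduction in symptoms. Section 8.1 says of the VAS item: "We would ask this same question both before and after the two week usage period". Section 12.1 calls Visit 5 a baseline for the third product. Neither period-end VAS nor change from period baseline is named as the analysed quantity.

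**The concern.** Section 19.1 itself treats carryover as something left over from the product of the previous phase. A model that accounts for it needs to know which product that was. Treatment x period does not carry this information: it lets the treatment difference vary by period, whatever was used before. It can stand in for carryover in a two-product, two-period crossover, but this trial has three products over three periods.

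At stake is a mislabelled estimate. If the preliminary test is significant, the report could present HYDRAL versus placebo and HYDRAL versus Biotene as adjusted for carryover when they hold about as much carryover bias as the unadjusted paired comparison. If it is not significant, the paired comparison is used with no check behind it, although moderate carryover could have gone undetected.

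**Working it through.** **Inputs from Section 19.1.** Two-sided level 0.025, 80% power, difference 0.8, 33 subjects needed, 39 recruited. No SD is given, so 33 can only be solved backwards. With a paired t test it implies an SD of the difference of 1.432, hence a within-subject SD of 1.432/√2 = 1.012. That SD gives 87% power at n=39.

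**Assumptions.** Period-end VAS, scored so that positive means more relief. Only HYDRAL carries over, by λ units, to the end of the next period. Bias is given per unit of λ for HYDRAL minus comparator. The order set is either all six orders, balanced, or one 3-order Latin square.

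**Step 1: paired test, by counting.** With six orders, placebo directly follows HYDRAL in 2 of 6, and so does Biotene. Each comparator mean rises by λ/3 and HYDRAL's own mean is unaffected, so both contrasts have bias -1/3. With the square H-P-B, P-B-H, B-H-P, placebo follows HYDRAL in 2 of 3 orders and Biotene in none: bias -2/3 on HYDRAL-placebo and 0 on HYDRAL-Biotene. The mirror square swaps them.

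**Step 2: the models, by generalised least squares expectation.** Six orders; correlations are for periods 1-2/1-3/2-3. Results are the same for both HYDRAL comparisons.

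| Estimator | Equal correlation | 0.6/0.36/0.6 | 0.3/0.5/0.7 |
|---|---|---|---|
| Paired test | -0.333 | -0.333 | -0.333 |
| Treatment + period | -0.333 | -0.456 | -0.307 |
| Plan's fallback, averaged over periods | -0.333 | -0.384 | -0.285 |
| Plan's fallback, period 1 contrast | 0 | -0.336 | +0.279 |
| Treatment + period + preceding product | 0 | 0 | 0 |

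The period 1 contrast picks up bias because, under an unstructured covariance, the period 1 estimates borrow from later periods that contain carryover.

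With one Latin square, under all three covariances, the fallback's averaged bias is -0.667 on one comparison and 0 on the other. Its period 1 contrast is unbiased, and so is the preceding-product model.

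**Step 3: scale.** Suppose the true difference is 0.8, with six orders and equal correlation. An assumed λ of 0.4 gives an expected fallback estimate of 0.8 - 0.4/3 = 0.67, and λ of 0.8 gives 0.8 - 0.8/3 = 0.53.

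**Step 4: change from period baseline.** If carryover is equal at baseline and period end, it cancels: bias 0. If it is present at baseline but gone by period end, the comparators' gains shrink by λ/3 and the bias becomes +0.333.

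**Step 5: what a non-significant preliminary test shows.** For the HYDRAL-carryover pattern over six orders, the within-subject sum of squares is 4 - 4/3 = 8/3. Removing period (4/9) and treatment (4/9) leaves 16/9, or 8/27 per subject. The noncentrality is (8/27)nλ²/1.012². For λ = 0.8 this is 6.11 at n=33 and 7.22 at n=39. An F test with 2 and 2n-6 degrees of freedom at an assumed 5% level has this power:

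| λ | n=33 | n=39 |
|---|---|---|
| 0.4 | 17% | 20% |
| 0.8 | 57% | 65% |
| 1.2 | 91% | 95% |

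If the within-subject SD is between 0.8 and 1.25, power for λ = 0.8 runs from 78 to 40% at n=33 and from 86 to 46% at n=39.

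**Step 6: precision of the corrected model.** Six orders, correlation 0.5: standard error 0.4537 against 0.4082 for treatment + period, a ratio of 1.11. The ratio is 1.213 and 1.070 in the two unstructured examples. With one Latin square it is 1.183/0.577 = 2.05.

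**The case against.** The strongest defence is that the bias may never arise. There is a one-week washout, and period-end VAS is taken about three weeks after the previous rinse was last used (one week of washout plus two of use). A reader might infer from the Section 12.1 remark "Since some mouthrinses have a residual effect on oral tissues" that carryover on the VAS is established. It is not: the remark concerns oral tissues and justifies the pre-screening withdrawal. This limits the size of the problem but does not rescue the model. The plan provides an analysis for the case where washout fails, and that analysis should do what it claims.

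Second, the -0.333 is not universal. It assumes six orders and period-end VAS. In a Latin square the fallback's period 1 contrast is free of carryover, and under change from baseline, a natural reading of the endpoint wording, the bias can vanish or change sign. All of this stands. It makes the magnitude conditional, but the plan neither fixes the orders nor selects the period 1 contrast. Nor should one conclude that no order list exists; the third party's codes may contain one.

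Third, a reader might infer that the two-stage rule inflates type I error by itself. It does not in the case checked: without carryover, simulated error was 2.4% against 2.5% nominal. The harm arises when carryover exists, because neither branch models it. Removing the preliminary test is therefore secondary.

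Fourth, a reader might infer that one treatment + period primary would cure the bias. It would not, and in the two unstructured examples its bias (-0.456 and -0.307) exceeds that of the fallback (-0.384 and -0.285).

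**Conclusion.** The concern holds in a limited form. The missing preceding-product term and the unnamed contrast are plain from Section 19.1 and need no assumption. The bias figures do: they take period-end VAS, carryover from HYDRAL only, and an assumed order set. On that footing the averaged fallback contrast keeps about a third of the carryover with six orders (-0.285 to -0.384 per unit), or two thirds on one comparison with a Latin square. That is about what the paired test keeps. The preliminary test cannot be relied on to detect carryover as large as the target difference. The documents do not support a claim that carryover is present, that the bias has one fixed size or sign, or that the trial's error rate is inflated without carryover. This should be corrected before the analysis is run, and the orders should be settled before randomisation.

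**What to change.** In the carryover model of Section 19.1, replace treatment x period with a first-order carryover term: the product used in the preceding period, with none in period 1. Name the HYDRAL-placebo and HYDRAL-Biotene contrasts from that model and its covariance structure.

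Report it as a pre-specified sensitivity analysis whatever the preliminary ANOVA shows. Do not describe a treatment + period or treatment x period estimate as carryover-adjusted.

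State that all six product orders are used, from a blocked list, and state whether the endpoint is period-end VAS or change from period baseline.

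Optionally, replace the two-stage choice by one pre-specified treatment + period primary, with a statement that this model does not itself remove carryover bias.

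The cost is wording and a blocked list (39 = 6 x 6 + 3, so one block is incomplete), with no extra subjects or visits. The preceding-product model's standard error is about 11% larger than that of treatment + period with six orders under equal correlation, and 7 to 21% larger in the two unstructured examples. With a single Latin square it would roughly double, which is the practical reason to fix the six orders in advance.

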20.0 Confidentiality*

A. Confidentiality of Study Data

Describe the local procedures for maintenance of confidentiality of study data and any records that will be reviewed for data collection.

20.1 A. *Where and how will all data and records be stored? Include information about: password protection, encryption, physical controls, authorization of access, and separation of identifiers and data, as applicable. Include physical (e.g. paper) and electronic files.*

Response: Data (paper records) will be stored at [name], School of Dental Medicine, University at Buffalo under the control of the PI and will be restricted by a lock-key that can only be accessed by members of the research team on this protocol.

All collected data will be on forms in which the subjects' identity is coded and the code can only be broken if an emergency situation occurs which requires knowledge of the product the subject is using. All data will only be available to study staff and to a biostatistician who will also not know identity. All data will be kept in a locked file cabinet in [name] (PI's office).

All patient identification will be by a coded-key (subject numbers). The code will be stored in a sealed envelope and stored in the PI's locked cabinet ([name]). The envelope will not be opened unless required by an emergency situation

related to product use by the patient. This form and all collected data will also be stored in a locked file cabinet in [name] (PI's office). All data collected electronically such as patients evaluations, patient excel log, and patient demographics will be stored in a password protected file on our clinical computer in our Center for Dental Studies.

20.2 A. *How long will the data be stored?*

Response: The data will be stored for duration of study, data analysis and possible publication (anticipated total of 6 months).

20.3 A. *Who will have access to the data?*

Response: PI and members of the research team.

20.4 A. *Who is responsible for receipt or transmission of the data?*

Response: PI

20.5 A. *How will the data be transported?*

Response: Data may be transported either through secure paper mail (USPS) or de-identified electronic for statistical analysis (off-site biostatistician).

B. Confidentiality of Study Specimens

*Describe the local procedures for maintenance of confidentiality of **study specimens**.*

- N/A: No specimens will be collected or analyzed in this research.
(Skip to Section 19.0)

20.6 B. *Where and how will all specimens be stored? Include information about: physical controls, authorization of access, and labeling of specimens, as applicable.*

Response: N/A

20.7 B. *How long will the specimens be stored?*

Response: N/A

20.8 B. *Who will have access to the specimens?*

Response: N/A

20.9 B. Who is responsible for receipt or transmission of the specimens?

Response: N/A

20.10 B. How will the specimens be transported?

Response: N/A

21.0 Provisions to Monitor the Data to Ensure the Safety of Subjects*

- N/A: This study is not enrolling subjects, or is limited to records review procedures only. This section does not apply.

NOTE: Minimal risk studies may be required to monitor subject safety if the research procedures include procedures that present unique risks to subjects that require monitoring. Some examples include: exercising to exertion, or instruments that elicit suicidality or substance abuse behavior. In such cases, N/A is not an acceptable response.

21.1 Describe the plan to periodically evaluate the data collected regarding both harms and benefits to determine whether subjects remain safe.

Response: In addition to the efficacy parameters, safety parameters will be collected by members of the research team. This will ensure a study with minimal risk to the participants and early detection of adverse reactions. If an adverse event occurs, the subject may be scheduled for a follow-up or under the direction of the Principal Investigator referred to a physician or dentist for treatment. Serious Adverse Events will be followed to the extent of resolution possible. The Principal Investigator will note the follow-up and resolution of Adverse Events on the Adverse Events Form (uploaded to click IRB). All serious or unsuspected adverse events will be reported to the IRB. Any Serious Adverse Events that occur during the clinical study period will be reported promptly by the Principal Investigator to the IRB within 24 hours of receiving the information.

21.2 Describe what data are reviewed, including safety data, untoward events, and efficacy data.

Response: Study personnel will make note of any health issues they observe or that the subject mentions spontaneously. Recording will include expected or unexpected Adverse Events such as illnesses, injuries, accidents, reactions to a concomitant medication, or worsening of a progressive disease state. An evaluation of the subject's extra- and intra- oral tissues will also be conducted to determine whether any visible adverse response to the test article occurred. In addition subjects will be queried about any other signs or symptoms they have noticed during the course of the study. Adverse events will be evaluated by the

Principal Investigator as to whether they were likely caused by the study mouthrinse and classified on the Adverse Events Form as related or unrelated to the study product. Adverse Events will also be classified as mild, moderate, or severe and reported by organ system.

21.3 Describe any safety endpoints.

Response: Adverse oral mucosal reactions.

21.4 Describe how the safety information will be collected (e.g., with case report forms, at study visits, by telephone calls with participants).

Response: Adverse events will be evaluated by the Principal Investigator as to whether they were likely caused by the study mouthrinse and classified on the Adverse Events Form as related or unrelated to the study product. Adverse Events will also be classified as mild, moderate, or severe and reported by organ system

21.5 Describe the frequency of safety data collection.

Response: At each study visit, the subject will be asked an open-ended question about whether he/she experienced any changes in general health or medication intake since the prior visit; the response will be recorded.

21.6 Describe who will review the safety data.

Response: PI

21.7 Describe the frequency or periodicity of review of cumulative safety data.

Response: At each study visit, the subject will be asked an open-ended question about whether he/she experienced any changes in general health or medication intake since the prior visit; the response will be recorded.

21.8 Describe the statistical tests for analyzing the safety data to determine whether harm is occurring.

Response: Safety will be assessed by subjective comments and oral hard and soft tissue exams. A comparison between test and placebo groups using a *t test* will allow us to compare any adverse effects occurring in the study.

21.9 Describe any conditions that trigger an immediate suspension of the research.

Response: No adverse reactions resulting in suspension of the research is anticipated. The products being tested are commercially available and have a 510(K) approval by FDA. However, if an adverse event occurs that the PI determines to (1) have a serious effect on the health and well-being of the subject

and/or (2) be treatment-related, the study will be suspended immediately and reported to the IRB as soon as possible. If the adverse event is determined to be treatment related, the study will not be resumed. without the approval of the IRB.

